6.2.2 Pre-Intervention Assessment

The pre-intervention assessment will be administered by trained evaluators and will take 1.5 hours.

- The Participant Characteristics Form will record age, sex, race, ethnicity, education, vocational status, residential status, social support, stroke characteristics, and stroke chronicity.
- The Self-Administered Comorbidity Questionnaire is a participant-reported measure of comorbidities. Participants are asked to report on the presence or absence of specific chronic diseases, if they receive treatment for the disease, and if the disease interferes with their daily life activities.
- The Montreal Cognitive Assessment is brief, standardized measure of cognitive function. Participants are asked to complete a series of cognitive tasks assessing attention, memory, visuospatial function, and selected executive function domains, and their performance is scored by a trained assessor.
- The Medical Outcomes Survey Social Support Survey is a brief questionnaire that assesses companionship, assistance and support from others.

- The PROMIS Ability to Participate in Social Roles and Activities 8-item short form will be the primary measure of community participation. The measure assesses difficulty participating in social roles and activities (1=always difficult, 5=never difficult).
- The PROMIS Satisfaction with Social Roles and Activities 8-item short form will be used to assess satisfaction with community participation (1=always satisfied, 5=never satisfied).
- The PROMIS Social Isolation 8-item short form will be used to assess perceptions of social isolation (1=never, 5=always).
- The PROMIS Global Health 43-item short form will be used to assess perceived global health (1=excellent health, 5=poor health).
- The Community Participation Indicators Scale is a detailed questionnaire that assesses the frequency of community participation activities, satisfaction, and degree of enfranchisement (belongingness) that individuals with stroke-related disability have with respect to community participation.
- The Community Participation Activation Scale is a brief questionnaire that assesses the active role that people with stroke-related disabilities take in engaging in community participation.
- The Participation Self-Efficacy Scale assesses confidence in understanding and managing one's community participation.
- The Chronic Disease Self-Efficacy Scale assesses confidence in understanding and managing one's health condition and associated symptoms.
- The Patient Activation Scale assesses the active role that people with take in managing their health and symptoms.
- The Sedentary Behavior Questionnaire asks participants to report time spent in 9 specific sedentary behaviors during a typical weekday and weekend. This assessment demonstrates validity and reliability for measuring sedentary behavior in the adult population.
- The Physical Activity Scale for Individuals with Physical Disabilities will measure self-reported physical activity. This questionnaire asks participants to report time spent in 13 types of physical activity over the past 7 days.
- ActivPAL(TM) monitors will be used to assess sedentary behavior and step count over 7 days. The ActivPAL is a small, lightweight monitor that quantifies time spent in sitting, reclined, standing, and stepping. The participant will be provided the "ActivPAL Guide" as a reference guide. We will follow a 24-hour wear protocol in which the participants will wear the device on their thigh for 7 days. A trained assessor will train the participant on appropriate care and use of the device. The ActivPAL will be waterproofed and fastened to the individual's thigh using a non-latex, gentle adhesive (Tegaderm). Prior to adhering the device, the assessor will conduct a gross sensation tactile localization screen to detect impairment in sensation on the participant's anterior thigh. The assessor will ask the participant to close their eyes and will lightly touch the participant's anterior thigh in the region where the ActivPAL will be positioned (anterior, upper half). He/she will ask the participant to indicate when and where the researcher touched. If impaired gross sensation is detected, or the participant reports sensitivity to adhesives, alternative strategies for positioning the device and alternate wear

schedules (such as removing the device during non-waking hours or wearing the device for fewer than 7 days) will be identified. Participants will also be asked to record their bedtime and waking time in the "ActivPAL Diary". Sedentary bouts, sedentary breaks, and steps per day will be assessed using the ActivPAL monitor.

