The self-management training will be administered by an occupational therapist and a peer-mentor in group sessions (social learning). Individual application of the self-management training content will be facilitated with guided skill development principles. The intervention will be 12 two-hour sessions, offered 2 times per week for 6 weeks, based on previous intervention dosing studies. There are limited known and potential risks because the intervention focuses on doing routine daily activities in the home and the community, as would normally be encountered in the course of everyday life. However, there is a minimal risk of frustration fatigue, fall, or injury that may result from increasing physical and social activity levels over the course of time. These risks will be minimized through supervision of licensed occupational therapists.

ADDENDUM: With the onset of the pandemic, we developed methods to deliver this intervention program remotely. People with stroke-related disability, particularly those in low income communities, face unique problems in the home and the community during pandemic conditions. We decided to add a second phase of the study, delivering the intervention remotely, to address these needs, and to compare metrics across phases (in person, remote).

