3. STUDY DESIGN

This is a multi-site, multi-phase single-arm community-based clinical trial examining the feasibility, acceptability, safety, and variation in changes in community participation attributed to ENGAGE among community-dwelling adults with mild to moderate stroke-related disability and low income. The 6 week intervention (12 two-hour sessions, 2 times per week) intervention will be delivered in community-based settings (in person) or in the home (remote), and assessments will be delivered in the home or community-based settings (in person) or via teleconference (remote). Assessments will be administered by independent evaluators at each site, and all data will be collected electronically and stored in REDCap, a cloud-based data management system accessible to all investigators at all sites.

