6.2.4 Post-Intervention Assessment

The post-intervention assessment will be administered by trained independent evaluators and will take 1 hour.

- PROMIS Ability to Participate in Social Roles and Activities
- PROMIS Satisfaction with Social Roles and Activities
- PROMIS Social Isolation
- PROMIS Global Health
- Community Participation Indicators Scale.
- Community Participation Activation Scale
- Participation Self-Efficacy Scale
- Chronic Disease Self-Efficacy Scale
- Patient Activation Scale
- Sedentary Behavior Questionnaire
- Physical Activity Scale for Individuals with Physical Disabilities
- ActivPAL(TM) (7 day wear)
- Client Satisfaction Questionnaire

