7. SAFETY ASSESSMENTS

7.1 Adverse Events

Given the benign nature of the intervention and assessment procedures, we anticipate minimal to no adverse events. Nonetheless we will monitor physical safety of participants during the intervention period, to assess the potential for adverse events.

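### The touch-based skin-sensation check before the ActivPAL is attached cannot be done as written in the teleconference phase, and active safety monitoring in 7.1 does not span the monitor-wear periods

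*Combined protocol and SAP*

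**What the plan says.** Section 6.2.2 sets out the fitting of the ActivPAL, an adhesive thigh monitor worn round the clock for 7 days. A check comes first: "Prior to adhering the device, the assessor will conduct a gross sensation tactile localization screen to detect impairment in sensation". The person doing the touching is study staff ("The assessor will ask the participant to close their eyes and will lightly touch the participant's anterior thigh in the region where the ActivPAL will" …), and afterwards "He/she will ask the participant to indicate when and where the researcher touched". If sensation is impaired, or the participant reports sensitivity to adhesives, the section calls for a different way of positioning the device or a different wear schedule. No other trigger is given.

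Section 3 sets the mode of assessment by phase: "assessments will be delivered in the home or community-based settings (in person) or via teleconference (remote"). The remote phase came later, by the addendum in section 2.2: "We decided to add a second phase of the study, delivering the intervention remotely". The same addendum says that metrics will be compared between phases.

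The schedule in 6.1 shows the ActivPAL before and after the intervention. The post-intervention list in 6.2.4 repeats it as "ActivPAL(TM) (7 day wear"). Neither place separates the phases.

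On safety, section 7.1 says that "we will monitor physical safety of participants during the intervention period". Sections 7.2 and 7.3 require any adverse event to go to the IRB immediately, and 7.3 adds a weekly safety review by the Executive Committee.

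**The concern.** The check needs physical contact between assessor and participant, and a teleconference does not allow it. A remote site that follows the text has two options, and the protocol chooses neither. It can fit the monitor without the check, in which case the impaired-sensation trigger can never operate. The other trigger, reported adhesive sensitivity, is not a substitute, because it does not detect loss of feeling. Or it can leave the monitor off, in which case device-measured step count and sedentary time are missing for that phase and the planned comparison between phases loses those measures. With several sites, different sites may resolve this differently.

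The people the check is written for are those who may not feel a skin problem under the dressing, and section 2.1 itself describes residual sensorimotor impairment after stroke. That makes the monitoring window in 7.1 relevant: if the check is skipped, active surveillance during wear is the next safeguard, and most or all of the wear lies outside the period that 7.1 names.

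**Working it through.** No figure in the plan bears on this point, so the check is a comparison of passages plus simple date arithmetic.

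**Can the check be done remotely as written?**
1. Section 6.2.2: the assessor touches the thigh, and the participant says when and where. Contact by study staff is required, and no phase is excepted.
2. Section 3: the home and community settings are labelled in person; the remote mode is teleconference. The home setting therefore does not supply a remote-phase visit.
3. Sections 6.1, 6.2.2 and 6.2.4, with the objectives in 1.2 and the addendum in 2.2: none drops the monitor in the remote phase, lets another person do the touching, or gives a remote version of the check.
4. The intervention manual is cited in 5.1, 5.2 and 5.4 for intervention delivery, adherence and fidelity, not for this assessment.

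Steps 1 and 2 cannot both be followed for a remote participant who wears the monitor, and steps 3 and 4 find no text that resolves it.

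**Which wear days fall in the period named in 7.1?**
Inputs: section 6.1 puts pre-intervention assessment at Day -14 to -1, intervention sessions at Day 0 to 42, and post-intervention assessment at Day 43 to 57. Section 7.1 gives no days, so I take its intervention period to be Day 0 to 42. I assume that fitting takes place within the assessment window and that the fitting day is the first wear day. Wear fitted on Day f then covers Day f to Day f + 6.

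- Post-intervention: the earliest fitting is Day 43, covering Day 43 to 49; the latest is Day 57, covering Day 57 to 63. Since 43 > 42, all 7 days fall outside.
- Baseline: all 7 days fall before Day 0 when f + 6 ≤ -1, that is f ≤ -7. A fitting on Day -7 covers Day -7 to -1. For later fittings the number of days before Day 0 is -f, from 6 (Day -6) down to 1 (Day -1, covering Day -1 to 5).
- Total for full wear: 2 × 7 = 14 days, of which between 7 + 1 = 8 and 7 + 7 = 14 fall outside Day 0 to 42.

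This second result does not depend on phase. It applies equally to in-person participants.

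**The case against.** Several points on the other side have force.

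- **Remote use of the monitor is inferred.** No sentence says that remote participants wear the ActivPAL. The inference rests on lists that do not separate phases and on the intention to compare metrics. It is the natural reading, but it remains an inference. The guide given to participants is not part of the documents and might say more.
- **Adverse events are still reportable.** A reader might infer that a skin injury during wear would go unrecorded. The documents do not support that: 7.2 and 7.3 set no time limit on reporting, and section 12 has the Executive Committee meeting weekly throughout the study. The gap is in active surveillance, not in the duty to report.
- **Little of the analysis is at stake.** A reader might infer that activity and sedentary outcomes as a whole would be lost, or that the main results are threatened. Neither follows. The Sedentary Behavior Questionnaire and the self-report physical activity scale are collected at both time points. Step count and sitting time are exploratory in 1.2. The primary benchmarks in 9.5.1 and the PROMIS Ability to Participate measure do not depend directly on the monitor.
- **A failed check does not bar wear.** It leads to another position or schedule, so it would be wrong to describe passing it as a condition of wearing the device. Nor is it established that remote participants would go straight to standard wear, since a site might leave the monitor off.
- **The NIHSS at screening covers sensory perception (6.2.1).** Nothing links that item to device placement, however, and 6.2.2 asks for its own check at the placement site.

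These points limit the consequence. They do not remove the conflict between section 3 and section 6.2.2.

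**Conclusion.** The concern holds in this limited form. A written safeguard cannot be carried out as described for an entire phase, and the text leaves sites to skip it or forgo device data. It looks like an inconsistency left when the remote phase was added, and it is worth correcting because it concerns participant protection and sites have no common instruction. Separately, the monitoring commitment in 7.1 misses all post-intervention wear and some or all of baseline wear: 8 to 14 of 14 days.

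The conclusion assumes that the monitor is meant to be worn remotely, that the 6.2.2 fitting steps also apply at the post-intervention fitting (6.2.4 gives none of its own), and that the intervention period means Day 0 to 42.

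A reader might want to go further and project how many participants would be harmed or fitted without detection of sensory loss. The documents give no rate of impaired thigh sensation, no skin-injury rate, and no split of the sample in 9.2 by phase, so no such number can be supported.

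**What to change.** 1. Reconcile sections 3 and 6.2.2 by stating whether, and if so how, the sensation check and the device fitting take place in the remote phase. The procedure is for the sponsor to choose; none is proposed here.
2. Add one REDCap field, completed at each fitting, recording whether the check was done and its result.
3. Extend the monitoring in 7.1 to both monitor-wear periods, in both phases, with one skin question when the device is returned.

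The cost is protocol wording, one data field and one question. There may also be less remote device data, depending on how the sponsor reconciles the passages: up to the whole remote phase if the monitor is dropped there. In that case the protocol should say that the comparison between phases on activity and sedentary behavior rests on the self-report scales.

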6.2.3 Blinding

There is no blinding in this single arm study. That said, independent evaluators will compete the post-intervention assessments.

6.2.4 Post-Intervention Assessment

The post-intervention assessment will be administered by trained independent evaluators and will take 1 hour.

- PROMIS Ability to Participate in Social Roles and Activities
- PROMIS Satisfaction with Social Roles and Activities
- PROMIS Social Isolation
- PROMIS Global Health
- Community Participation Indicators Scale.
- Community Participation Activation Scale
- Participation Self-Efficacy Scale
- Chronic Disease Self-Efficacy Scale
- Patient Activation Scale
- Sedentary Behavior Questionnaire
- Physical Activity Scale for Individuals with Physical Disabilities
- ActivPAL(TM) (7 day wear)
- Client Satisfaction Questionnaire

7. SAFETY ASSESSMENTS

7.1 Adverse Events

Given the benign nature of the intervention and assessment procedures, we anticipate minimal to no adverse events. Nonetheless we will monitor physical safety of participants during the intervention period, to assess the potential for adverse events.

7.2 Reporting Procedures

Any adverse events will be reported to the IRB immediately and documented in the regulatory binder.

7.3 Safety Monitoring

The Executive Committee will meet weekly to review participant safety. Any adverse events will be reported to the IRB immediately and documented in the regulatory binder.

8. INTERVENTION DISCONTINUATION

There are no foreseeable circumstances that may result in intervention

discontinuation, barring unforeseen medical events prohibiting participation (e.g., recurrent stroke).

9. STATISTICAL CONSIDERATIONS

9.1 General Design Issues

This pilot study is a descriptive study. Data will be plotted visually and characterized through descriptive statistics with appropriate indices of variation when indicated.

9.2 Sample Size and Randomization

Given the focus on feasibility and the prematurity of hypothesis testing, we estimated the sample needed to assess feasibility of a multi-site implementation of the intervention protocol. With a minimum of 20 participants per site we will have a sufficient sample to examine feasibility, acceptability, safety, and the range in magnitude of change in community participation measures within each site (Cohen's d). With 60 participants, we will have 80% power to detect a moderate effect (Cohen's $d=0.37$) of within-participant change using a two-tailed paired samples t-test with $\alpha=0.05$. Our pilot studies' effect sizes ranged from $d=0.37$ to 0.97 and our detectable effects fall within this range.

9.3 Definition of Populations

All participant data will be analyzed regardless of study completion.

9.4 Interim Analyses and Stopping Rules

Given the pilot phase of this study and the benign nature of the intervention and the intended outcome, no interim analyses or stopping rules will be used.

9.5 Outcomes

9.5.1 Primary Outcome

Feasibility will be indicated by >90% of target enrollment, >90% retention, and >90% intervention fidelity at each site; acceptability will be indicated by >90% participant satisfaction at each site; and safety will be indicated by <3% participants with a reportable event (i.e., injurious fall) at each site, and by phase.

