6.2 Description of Evaluations

6.2.1 Screening Assessment

The screening assessment will be administered by trained evaluators and will take 1 hour.

- The National Institutes of Health Stroke Scale is a valid and reliable scale to assess neurological impairment associated with stroke. Items test alertness, orientation, command following, eye and limb movements, vision, language and sensory perception.
- The Activity Card Sort is a valid and reliable assessment of community participation.
- The Boston Diagnostic Aphasia Examination severity scale assesses aphasia impairment severity in three domains: comprehension, expression, and fluency.
- The PRIME-MD with Mini-Neuropsychiatric Interview module assesses presence of mood disorders.

N. B. As part of the assessment of mood, we are including items to address risk of suicidality, a potential risk associated with depression. This action was advised by a physician co-investigator and geriatric neuropsychiatrist [name], who advises all assessments of depression including these items. If in the course of assessment it is determined that an individual has either major depressive disorder or suicidality, we will 1) refer the participant to local services (in Pittsburgh, the RESOLVE Crisis Network, a 24 hour service that directs individuals with major depressive disorder and/or suicidality to immediate care), 2) notify the contact person identified by the participant, and 3) notify the treating physician on service at the time of referral. We will document these actions in the study records. This 3-step plan has been effective when we encountered major depressive disorder in our previous studies with this population (over the last 10 years).

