9.6 Data Analyses

We will conduct descriptive analyses to address the feasibility, acceptability, and safety benchmarks in the primary aim. We will examine univariate and bivariate distributions of variables, and plot community participation scores to visually

characterize changes in community participation within and between sites to address the secondary aim. We will also calculate within subjects change in community participation as well as Cohen's d effect sizes of change for both sites combined, and each site.

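### The site safety verdict counts injurious falls only, so a site of 20 with a serious non-fall injury and no injurious fall would be called safe at 0%

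*Combined protocol and SAP*

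**What the plan says.** Section 9.5.1 sets the criterion: "safety will be indicated by <3% participants with a reportable event (i.e., injurious fall) at each site", and adds that it is also judged by phase. Section 1.1 gives the same definition, without the mention of phase.

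On risk, Section 2.2 states that "there is a minimal risk of frustration fatigue, fall, or injury that may result from increasing physical and social activity levels". Section 7.1 commits to monitoring physical safety in general while the intervention runs, which the schedule in Section 6.1 places at Day 0 to 42.

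On recording, Section 7.2 is broad: "Any adverse events will be reported to the IRB immediately and documented in the regulatory binder". Section 7.3 repeats this and adds weekly review by the Executive Committee.

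On analysis, Section 9.6 offers one sentence: "We will conduct descriptive analyses to address the feasibility, acceptability, and safety benchmarks in the primary aim". No section plans to tabulate or summarise adverse events outside the benchmark.

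On size, Section 9.2 plans "With a minimum of 20 participants per site" and 60 in total.

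**The concern.** The criterion and its label do not match. What is measured is injurious falls; what is concluded is that a site was safe. The protocol itself lists injury separately from a fall among the risks of raising physical and social activity, so the missing harm is one it attributes to its own intervention.

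Nothing in the planned analysis makes up the difference. A non-fall injury would be reported and filed, but Section 9.6 gives it no place in the results. Section 9.4 provides no interim analysis or stopping rule, so the benchmark is the plan's only formal statement on safety. If the plan is followed exactly, a site where a participant is seriously hurt other than by falling is reported as meeting the safety benchmark, with no planned table that would show the reader otherwise. What is at stake is what this pilot may claim about safety, by site and by phase, when it informs later studies.

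**Working it through.** **The plan's own figure.** The documents give no operating characteristics for the safety benchmark. The only sample-size figure is in Section 9.2: 80% power for a two-sided paired t-test with N = 60, d = 0.37 and alpha = 0.05. From the noncentral t distribution with 59 degrees of freedom and noncentrality 0.37 × √60 = 2.87, power is 80.5%, so the figure reproduces. It has no bearing on the safety benchmark.

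**Inputs.** Limit: below 3% of participants (Sections 1.1 and 9.5.1). Site size: n = 20, a stated minimum (Section 9.2). Sites: three (Section 1.1 names three cities; 60/20 = 3). Event rates: none given.

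**Step 1: what <3% allows at 20.** 0.03 × 20 = 0.6 of a person. So 0/20 = 0% passes and 1/20 = 5% fails: no counted event is allowed.

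**Step 2: how far this depends on n = 20.** One event passes only if 1/n < 0.03, that is n > 33.3. At n = 33, 1/33 = 3.03% fails; at n = 34, 1/34 = 2.94% passes. One event therefore fails any site of up to 33. If a site is split by phase its denominators shrink, and one event still fails. If phase is instead judged across all sites, a phase with 34 or more participants could absorb one event.

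**Step 3: the two counts at a site of 20.**

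| Events at the site (different participants) | Injurious falls only | Falls or other injuries |
|---|---|---|
| None | 0/20 = 0%, pass | 0/20 = 0%, pass |
| One serious non-fall injury, no injurious fall | 0/20 = 0%, pass | 1/20 = 5%, fail |
| One injurious fall, one non-fall injury | 1/20 = 5%, fail | 2/20 = 10%, fail |

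The verdicts differ only in the second row, where there is no injurious fall.

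**Step 4: the price of a wider count.** If each participant independently has a counted event with probability p, a site of 20 has none with probability (1 − p)^20, and all three sites have none with probability (1 − p)^60. The rates are assumptions.

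| Assumed p | One site of 20 has none | All three sites have none |
|---|---|---|
| 1% | 0.99^20 = 82% | 0.99^60 = 55% |
| 2% | 0.98^20 = 67% | 0.98^60 = 30% |
| 3% | 0.97^20 = 54% | 0.97^60 = 16% |

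**The case against.** The strongest reply is that the text is consistent. Sections 1.1 and 9.5.1 give one definition twice, and the parenthesis fixes it as injurious falls. This stands. A reader might infer that Section 7.2 supplies a rival definition, because it makes every adverse event something to report. It does not: it is a reporting duty, it does not use the outcome's term, and such a duty may properly be wider than an outcome. Nor do the documents suggest that the definition would be chosen after events are known, or that the phases would be counted differently.

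A reader might also want to add other harms to the count. Two do not belong there:

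- **Suicidality.** The referral plan in Section 6.2.1 applies when "it is determined that an individual has either major depressive disorder or suicidality", and that is a screening procedure before the intervention. Current major depression is an exclusion (Section 4.2), and the post-intervention battery in Section 6.2.4 contains no mood instrument that would detect it.
- **Recurrent stroke.** Section 8 mentions it as an example of an unforeseen medical event, and Section 2.2 does not list it as a risk of the intervention. Counted without a relatedness rule, one background event in people with chronic stroke would fail a site of 20. It belongs in a table, not in the criterion.

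Three further points are fair. Failing on a single event comes from a 3% limit on a small denominator, whatever the definition. The study is a descriptive single-arm pilot in which few or no adverse events are expected (Sections 7.1 and 9.1). And participant protection does not depend on the benchmark, given IRB reporting, weekly review and supervision by licensed therapists.

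None of this answers the remaining point: a fall count, however clearly defined, does not support a general statement that a site was safe when non-fall injury is a named risk and is not otherwise analysed.

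**Conclusion.** The concern holds in a limited form. The stated rule is unambiguous but too narrow for the safety conclusion drawn from it: it omits non-fall injury, and Section 9.6 plans nothing to show what was omitted. The size is one event. At 20 per site, one serious non-fall injury at a site with no injurious fall separates a 0% pass from a 5% fail, and the same is true of any site up to n = 33.

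That result rests only on the stated limit and site size. How often the case would arise cannot be said, because the documents give no event rates; the probabilities in the working rest on assumed rates and independence between participants, and serve only to price the wider definition. A reader might infer that the plan contradicts itself or leaves participants unprotected. The documents support neither. The change is worth making because safety is part of the primary objective and the wording decides what may be claimed.

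**What to change.** In Sections 1.1 and 9.5.1, take one of two routes:

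1. Define the counted event as *an injurious fall or other injury needing medical care during the intervention period (Day 0 to 42)*, and keep the <3% limit.
2. Rename the outcome *injurious falls*, keep the <3% limit, and do not call a site safe on that count alone.

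With either route, add to Section 9.6 a descriptive table of all adverse events documented under Section 7.2, including any recurrent stroke, by type, site and phase.

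**Cost.** Wording in three sections and one table. The events are already to be documented, so the added work is recording type, date, site and phase in REDCap and, under route 1, whether an injury needed medical care. Route 1 makes the benchmark slightly harder to meet: if the counted rate rose from an assumed 1% to 2%, the chance of no event at a site of 20 would fall from 82% to 67%. Route 2 leaves the benchmark as hard to meet as now but limits the claim.
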